5.3.3 Primary Efficacy Endpoint

Estimand 1 (treatment policy strategy): The difference in change from baseline CDR-SB scores in subjects assigned to BIIB092 group in the PC period, comparing to late start BIIB092 group, regardless what actual treatment is received acknowledging a participant may miss more than four infusions, consecutively, change AD symptomatic medication and/or discontinue treatment early

- Analysis set: all subjects in the FAS
- Variable: The change from baseline CDR-SB scores at the week of interest regardless of intercurrent events (ICEs)
- Analysis set level summary: Least square (LS) mean difference from MMRM model in change from baseline between BIIB092 and placebo
- ICEs and Strategies for Addressing ICEs:

ICEs include

- AD symptomatic medication change (treatment policy strategy)
- Treatment discontinuation (treatment policy strategy)
- Missing more than or equal to four infusions consecutively (treatment policy strategy)

Since a treatment policy strategy will be used for all ICEs in this estimand, all observed data will be included regardless of miss more than or equal to four infusions consecutively, treatment discontinuation or AD symptomatic medication change. At LTE interim analysis, the primary

CONFIDENTIAL

The information contained herein may not be used, disclosed, or published without the written consent of Biogen MA Inc.

	Statistical Analysis Plan Long-Term Extension Period	V1.0
---	--	-------------

analysis is the mean difference of the change from baseline CDR-SB scores at Week 104 between treatment groups in the FAS who have a baseline and at least one post-baseline CDR-SB score [ICH E9 (R1) Addendum 2014, 2017]. At final analysis, the primary analysis is the mean difference of the change from baseline CDR-SB scores at the week of interest between treatment groups in the FAS who have a baseline and at least one post-baseline CDR-SB score. All observed data will be included in the primary analysis, including data collected after intercurrent events [ICH E9 (R1) Addendum 2017], i.e., treatment discontinuation or a change in concomitant use of AD symptomatic medication

The baseline and change from baseline CDR-SB scores at each post-baseline visit will be summarized by LTE treatment group. A mixed model with repeated measures (MMRM) will be used to analyze changes from Baseline in CDR-SB as described in [Section 5.3.2.1](#). A line plot of adjusted mean change from baseline over time will be provided.

5.3.4 Exploratory Efficacy Endpoints

The clinical endpoints assessing AD progression from Baseline include the results of the MMSE, ADAS-Cog13, ADCS-ADL, ISLT, eCog, FAQ, NPI-10, EMACC (composite score of ISLT, DKEFS, DSST, and Trails A), ADCOMS (composite score of selected items from CDR, MMSE, and ADAS-Cog 13) and iADRS.

The by visit summary and MMRM analysis will be performed for MMSE, ISLT, eCog, ADCS-ADL, FAQ, ADAS-Cog-13 (13-item), NPI-10, EMACC, ADCOMS, and iADRS as described in Section 5.3.2.1. For LTE interim analysis at PC DBL, all available records up to week 104 will be analyzed in MMRM table. The baseline and change from baseline scores at each post-baseline visit will be summarized by LTE treatment group at final analysis.

5.4 Safety Analyses

5.4.1 General Considerations

5.4.1.1 Analysis Population

The safety analysis set will be used for safety analyses of AEs, SAEs, clinical laboratory data, Columbia Suicide Severity Rating Scale (C-SSRS) data, ECG data and vital sign data. The safety MRI evaluable set will be used for the analysis of safety MRI data.

5.4.1.2 LTE Safety Treatment Groups

Since all the subjects are supposed to receive active treatment in LTE, the LTE safety treatment groups which are the same as the LTE treatment groups will be used for all the safety analyses.

CONFIDENTIAL

The information contained herein may not be used, disclosed, or published without the written consent of Biogen MA Inc.

5.4.1.3 Incidence, Incidence Proportion and Incidence Rate

- Incidence and incidence proportion will be provided in incidence proportion tables. Incidence is defined as the number of subjects who experienced an event. Incidence proportion is defined as the number of subjects who experienced an event divided by total number of subjects in the analysis population, i.e., percentage. Each subject will be counted only once within each category.
- Incidence and incidence rate will be provided in incidence rate tables. Incidence rate of an event based on the entire follow-up time – defined as the number of subjects who experienced an event divided by the total of entire follow-up time among the subjects in the analysis set (e.g., incidence rate per 100 subject-years). The entire follow-up time for a subject (subject-years) is defined as the sum of all subjects' follow-up time, where a subject's follow-up time is calculated as the number of days (inclusive) from first dose of study drug until the last day on study, divided by 365.25. Each subject will be counted only once within each category.

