16.10. Sample Size Considerations

There was no formal sample size calculation for the primary endpoint of safety.

The planned sample size is 528 participants, randomized in a 1:1:2:2 ratio, with 88 participants assigned to the BIIB092 low-dose group (44 assigned to 125 mg once every 4 weeks and 44 assigned to 375 mg once every 12 weeks), 88 participants assigned to the medium-dose group (600 mg once every 4 weeks), 176 participants assigned to the high-dose group (2000 mg once every 4 weeks), and 176 participants assigned to the placebo group. This sample size provides approximately 80% power to detect a dose-response relationship in the change from baseline in CDR-SB (primary efficacy endpoint) at 18 months (Week 78), assuming a mean change of 1.99 from baseline in CDR-SB at 18 months in the placebo group and a common SD of 2.38, a maximal 40% reduction for the highest BIIB092 dose group compared with the placebo group, and an estimated 20% dropout rate at 18 months (Week 78) in this study. Six different dose-response relationships will be tested at the 2-sided 5% significance level, using the MCP-MOD method to control for multiplicity [Bretz 2005]. Optimal contrasts will be constructed to detect potential dose-response trends under common dose-response curves (e.g., Emax, exponential, logistic, linear in log dose, and quadratic model) which are illustrated with the parameters shown in Figure 2.

The mean and SD of the change from baseline in CDR-SB at 18 months for the placebo group is based on available Alzheimer’s Disease Neuroimaging Initiative (ADNI) data from ADNI 1, ADNI 2, and [REDACTED].

[REDACTED]

[REDACTED]

[figure not shown]
[REDACTED]

CONFIDENTIAL

The information contained herein may not be used, disclosed, or published without the written consent of Biogen MA Inc.

In the LTE period, the actual sample size, [REDACTED], is dependent on the enrollment rate, and thus, sample size calculation is not needed.

Figure 2: Dose-Response Shapes Based on Clinical Dementia Rating Scale – Sum of Boxes Mean Change from Baseline at Week 78

ED₅₀ = median effective dose; Emax = maximum response

Note: This figure was generated using ADDPLAN[®] DF Version 3.1.8, by Aptiv solutions.

CONFIDENTIAL

The information contained herein may not be used, disclosed, or published without the written consent of Biogen MA Inc.

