2 DESCRIPTION OF LONG-TERM EXTENSION (LTE) OBJECTIVES AND ENDPOINTS

2.1 Primary LTE Objective and Endpoint

The primary objective for the long-term extension (LTE) period is to evaluate the long-term safety and tolerability of BIIB092 in participants with MCI due to AD or with mild AD.

The primary safety endpoint that relates to this objective is the incidence of AEs and SAEs over the placebo-controlled period and LTE period of the study.

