3.2 Analyses Period

Depending on the purpose, different analyses will be conducted on the following study periods:

1. LTE period. Only data in the LTE period will be included in these analyses. This LTE analysis period will be applied to all the AE analyses, and the analyses will include all subjects who were dosed in the LTE period.
2. Placebo-controlled and LTE period. All the data in the placebo-controlled and LTE periods will be included in these analyses. This analysis period will be applied to analyses including, but not limited to all efficacy analyses and listings. The analyses will include all subjects who were dosed in the study including those who did not enroll into the LTE period. For example, line plot of CDR sum of box mean change from baseline over time. in the placebo-controlled and LTE period.
3. Placebo-controlled and LTE active treatment period. Active treatment period is defined as the study period(s) that a subject received BIIB092. For early start subjects – subjects who received BIIB092 in both placebo-controlled and LTE period, all the data (placebo-controlled and LTE periods) will be included in the analyses. For late start subjects – subjects who received placebo in the Placebo-controlled period and BIIB092 in the LTE period, only data in the LTE period will be included. This analysis period will be applied to majority of safety tables, and the analyses will include all subjects who were dosed in the study except for subjects who received only placebo in the placebo-controlled period and did not get dosed in the LTE period. An example is the incidence rate of adverse events in the placebo-controlled and LTE active treatment period.

Subjects to be included in a certain output is determined by both the analysis set and the analysis period. For example, the incidence table of adverse events in the LTE period will include subjects in the safety population for the LTE period, i.e., all randomized subjects who received at least one dose of study treatment in the LTE period. The incidence rate table of adverse events in the placebo-controlled and LTE active treatment period will include subjects in the safety population for the active treatment period, i.e., all randomized subjects who received at least one dose of study treatment in the active treatment period. In this SAP we do not separately define the analysis set in each analysis period.

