5.2.4 Study Drug Exposure and Study Drug Compliance

A summary table of study drug exposure and compliance in the placebo-controlled and LTE active treatment period will be provided. Number of infusions (BIIB092) received will be summarized as a categorical variable (categories as integers from 1 to 20, and 1-5, 6-10, 11-15, 15-20, 21-26) as well as a continuous variable. Number of weeks on study treatment (BIIB092), calculated as $(\text{date of last dose} - \text{date of first dose} + 1) / 7$, will be summarized as a categorical variable (every 8 weeks from 0 to ≥ 96 weeks) as well as a continuous variable. Percentage of study treatment taken up to the last dose, calculated as $(\text{the actual number of infusions} / \text{by the number of infusions a subject is expected to take until the date of last infusion}) * 100$, will be summarized as a continuous variable. This table will be presented only by LTE treatment group. Similar outputs will also be generated for LTE period.

A listing of study drug administration records will be provided for the combined placebo-controlled and LTE period.

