5.4.2.1 Summary and Incidence Analysis

Overall summary of AE table will be done for the LTE period and placebo-controlled and LTE active treatment period, presented by LTE treatment group. The following information will be summarized: the number of subjects with any AE, with any AE by maximum severity, the number of subjects with any related AE (related to study drug as assessed by investigator), the number of subjects with SAE, the number of subjects with related SAE, the number of subjects with AE leading to drug withdrawal, the number of subjects with AE leading to study withdrawal, and the number of subjects with a fatal event.

The sorting order of AE incidence tables, unless otherwise specified, will be by decreasing frequency order of “BIIB092 total” column within each category in the tables presented by LTE treatment group. A subject is counted only once within each category in each table. For example, for the table of AEs by system organ class and preferred terms sorted by decreasing frequency presented by LTE treatment group, system organ class will be presented in decreasing frequency order of BIIB092 total column, and within each system organ class, preferred terms will be presented in decreasing frequency order of BIIB092 total column. A subject is counted only once within each system organ class and preferred term.

CONFIDENTIAL

The information contained herein may not be used, disclosed, or published without the written consent of Biogen MA Inc.

The following AE incidence tables will be provided for the LTE period. Selected tables (marked with *) will be presented for incidence rate of AEs for the placebo-controlled and LTE active treatment period:

1. AEs by system organ class and preferred term sorted by decreasing frequency *
2. AEs by system organ class and preferred term sorted by alphabetical order
3. AEs by system organ class *
4. AEs at least 2% higher in incidence by system organ class and preferred term for early start BIIB092 2000 mg/4wk compared to late start BIIB092 2000 mg/4wk presented only for LTE period
5. AEs by preferred term *
6. AEs by preferred term with an incidence of 5% or more

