5.4.2.2 Incidence Rate Analysis

Incidence rate of AEs based on the entire follow-up time for subjects with at least 1 AE in LTE period may be summarized by system organ class and preferred terms. The incidence rate tables will be presented by LTE treatment group. The entire follow-up time for LTE period is from the first dose in LTE period until the last day on study.

Follow-up adjusted incidence rate of AEs may also be summarized for placebo-controlled and LTE active treatment period, due to the different length of placebo-controlled and LTE active treatment period in early start versus late start high-dose BIIB002 subjects. The entire follow-up time is from the first dose in active treatment period (placebo-controlled period first dose of BIIB092 for early start subjects and LTE period first dose of BIIB092 for late start subjects) until the last day in the study.

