5.6.2 Structural MRI Analysis

No subjects reached week 226, the primary analysis timepoint for structural MRI. Therefore, structural MRI is not reported or statistically analyzed for the LTE period.

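### In the active-treatment-period tables the AE incidence rate counts each subject once but divides by all follow-up, so for common AEs it does not equalise early-start and late-start follow-up

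*SAP*

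**What the plan says.** SAP 5.4.1.3 gives the incidence rate as "defined as the number of subjects who experienced an event divided by the total of entire follow-up time among the subjects in the analysis set". A subject's follow-up runs from first dose to last day on study, and a subject counts once in each category however many events occur. Nothing in the SAP stops the clock at the first event.

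SAP 5.4.2.2 calls this rate follow-up adjusted in the combined active treatment period and gives the reason: "due to the different length of placebo-controlled and LTE active treatment period in early start versus late start high-dose" subjects. Early-start follow-up begins at the first BIIB092 dose in the placebo-controlled period, late-start follow-up at the first LTE dose.

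SAP 5.4.2.1 lists 20 AE tables for the LTE period. The starred ones (items 1, 3, 5, 9, 10, 11, 13, 14 and 15) "will be presented for incidence rate of AEs for the placebo-controlled and LTE active treatment period". SAP 3.2 says that for early-start subjects "all the data (placebo-controlled and LTE periods) will be included in the analyses". The primary LTE endpoint in SAP 2.1 is "the incidence of AEs and SAEs over the placebo-controlled period and LTE period of the study".

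**The concern.** After a subject's first event in a category, that subject adds person-time but can add nothing to the numerator. The longer the follow-up, the larger the share of such time, so the rate drifts down with follow-up even when the risk is constant. Follow-up length is exactly what separates early start from late start, and exactly what the rate is meant to take out.

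The starred tables matter because, apart from the overall AE summary and the COVID-19 tables, they are the only AE tables by system organ class and preferred term planned across both periods, the span that the primary LTE endpoint covers. For frequent AEs a reader would see a lower rate in the group exposed longer, which is the wrong direction of error for a long-term safety objective. A real excess in early start could also be hidden.

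**Working it through.** The documents give no AE rate, so there is no planned figure to reproduce. The check asks what the SAP's formula returns when both groups have the same true hazard.

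**Formulae.** With constant first-event hazard λ per year and follow-up of T years for everyone:
- rate as defined in SAP 5.4.1.3 = (1−exp(−λT))/T
- rate with person-time ended at first event = λ, whatever T is

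As λT becomes large, the SAP rate tends to 1/T and measures only follow-up length.

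**Follow-up** (days inclusive, divided by 365.25; late start begins on Day 561, Week 80):
- *Planned length, to Week 238:* early 1667 days (4.56 y); late 1667−561+1 = 1107 days (3.03 y). This is an upper bound, because SAP 5.6.2 states: "No subjects reached week 226, the primary analysis timepoint for structural MRI".
- *26 infusions:* SAP 5.2.4 groups infusions as "categories as integers from 1 to 20, and 1-5, 6-10, 11-15, 15-20, 21-26". Twenty infusions fall in the placebo-controlled period, so the 26th is at Week 100 (Day 701). Adding the follow-up visit 98 days later gives early 799 days (2.19 y) and late 799−561+1 = 239 days (0.65 y).
- *Cut at Week 104:* early 729 days (2.00 y); late 729−561+1 = 169 days (0.46 y).

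**Early/late ratio of the SAP rate, truth 1.00:**

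| First events per 100 subject-years | Planned | 26 infusions | Week 104 |
|---|---|---|---|
| 1 | 0.99 | 0.99 | 0.99 |
| 10 | 0.93 | 0.93 | 0.93 |
| 50 | 0.76 | 0.71 | 0.71 |
| 100 | 0.69 | 0.55 | 0.54 |

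Worked example, 26 infusions and λ = 1:
- early: (1−exp(−2.188))/2.188 = 0.888/2.188 = 0.406, or 40.6 per 100 subject-years
- late: (1−exp(−0.654))/0.654 = 0.480/0.654 = 0.734, or 73.4 per 100 subject-years
- ratio: 40.6/73.4 = 0.55

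The distortion passes 10% at about 14 to 15 first events per 100 subject-years.

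**Masking.** If the early-start hazard is truly double (1.0 against 0.5 per year), the reported ratio is 0.95 in the 26-infusion case and 0.97 at Week 104.

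**Dropout.** Protocol 16.10 assumes "an estimated 20% dropout rate at 18 months (Week 78) in this study". As an exponential rate this is −ln(0.8)/(547/365.25) = 0.149 per year. Applied from first BIIB092 dose in both groups, the ratios at 100 per 100 subject-years become 0.76 (planned), 0.58 (26 infusions) and 0.57 (Week 104). A simulation of 400,000 subjects per group agreed, and the time-at-risk rate gave 1.00 to 1.01 in all three cases.

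**Early-start subjects who never enter the LTE.** They stay in the early-start group, whereas late start holds only subjects dosed in the LTE. Assuming 20% or 40% of early start stop by Day 631, on top of that dropout, the ratios at 100 per 100 subject-years are 0.82 or 0.91 (planned) and 0.60 or 0.61 (26 infusions).

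**The case against.** The text and the arithmetic are not in dispute; the case on the other side is about weight.

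- **The primary endpoint does not depend on the rate.** SAP 5.4.1.3 defines incidence as a count of subjects, and the overall AE summary reports such counts for the active treatment period. This stands, but that summary has no breakdown by system organ class or preferred term.
- **The rate tables also show subject counts.** In the 26-infusion example these correspond to about 89% of early start and 48% of late start, the opposite direction to the rate. True, but two numbers that err in opposite directions do not give the reader a correct comparison.
- **The reach is limited.** Five of the nine starred tables concern severe AEs or SAEs, where most rows are rare. Four of the five dose groups share the early-start clock, so only contrasts with late start suffer. The one table naming an early-versus-late comparison (item 4) is LTE-only. All of this stands.
- **The wording is permissive.** SAP 5.4.2.2 says these rates may be produced, but SAP 5.4.2.1 commits to the starred tables.
- **The short scenarios are inferred.** Week 104 limits efficacy data at the interim analysis, not AE follow-up, and 26 infusions is read off table categories. They are illustrations. LTE non-entry does soften the planned-length figure, as shown above, but hardly moves the short ones.
- **Time at risk is not a complete cure.** If hazards vary between subjects (gamma frailty with variance 0.5 to 1, mean hazard 1 per year, 26-infusion case), the time-at-risk ratio is 0.84 to 0.75. The SAP rate gives 0.53 to 0.52 in the same setting, so most of the bias goes.

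**Conclusion.** The concern holds. As written, the rate does not do what SAP 5.4.2.2 wants from it when events are common: it over-corrects, and favours the group followed longer. With equal constant hazards the early-start rate reads 24% to 29% too low relative to late start at 50 first events per 100 subject-years, and 31% to 46% too low at 100, across the three follow-up cases. At 10 per 100 the shortfall is 7%, and at 1 per 100 about 1%.

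The result rests on assumed hazards that are constant and equal, on common nominal follow-up within each group, and on early-start events from the placebo-controlled period being counted, as SAP 3.2 states. How many rows reach the affected range cannot be known from the documents. The tables are descriptive, with no test, and LTE-only tables start every group at the first LTE dose, so they are little affected. The definition should be changed, but no inferential conclusion depends on it.

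**What to change.** For the starred active-treatment-period tables, redefine the rate in SAP 5.4.1.3 and 5.4.2.2 as subjects with the event divided by person-time at risk: from first BIIB092 dose to first occurrence in that category, or to last day on study if there is none. Keep the entire-follow-up rate as a supplementary display if wanted, and leave the LTE-period tables as they are.

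SAP 5.4.2 dates treatment emergence from the first LTE infusion. The revised text should confirm that early-start events from the placebo-controlled period count in these tables, as SAP 3.2 implies; otherwise their time would be in the denominator without their events.

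The cost is SAP wording and programming. Each system organ class and preferred term row needs its own time at risk, from onset dates already collected. Rates will be somewhat higher than under the current formula, and the groups are fully equalised only if the hazard is roughly constant over time since first BIIB092 dose.

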5.4.2 Clinical Adverse Events

Treatment-emergent AEs (TEAE)

A treatment-emergent AE is defined as AE that started or worsened after the start of first infusion of study treatment in LTE period.

First dose for below definitions is the first dose in LTE period

To define treatment emergence for AEs with missing start or stop date or time the following additional criteria will be used:

- if both the start and stop dates for a particular AE are missing, then that AE is considered treatment emergent;
- if the start date for a particular AE is missing and the stop date/time falls after the first dose date/time, then that AE is considered treatment emergent;
- if the start date for a particular AE was the same as the first dose date, and the start time was missing and stop time is after the first dose or missing, then that event is considered treatment emergent.

For AEs with a partial start date, the following imputation method will be used to determine if the event is treatment emergent:

- When only the day is missing, and the year/month is equal to the year/month of first dose date, and the AE stop date is missing or on/after the first dose date, then use the first dose date as AE start date. Otherwise impute the AE start date as the first day (1) of the AE start month
- When the AE start month is missing, and the year equals to the year of first dose date, and the AE stop date is missing or on/after the first dose date, then use the first dose date as AE start date. Otherwise impute the AE start date as the first day (01January) of the AE start year

CONFIDENTIAL

The information contained herein may not be used, disclosed, or published without the written consent of Biogen MA Inc.

	Statistical Analysis Plan Long-Term Extension Period	V1.0
---	---	-------------

For AEs with a partial end date, the following imputation method will be used:

- When only the day is missing, and the year/month equal to the year/month of the last date on study, then use the last date on study as AE stop date. Otherwise impute the AE stop date as the last day of the AE stop month
- When the AE stop month is missing, and the year equals to the year of last date on study, then use the last date on study as AE stop date. Otherwise impute the AE stop date as the last day (31December) of the AE stop year

Only TEAEs will be included in the tables, unless otherwise specified. All SAEs (including pre-dosing SAEs) will be included in the listing of SAEs, with an indicator of pre-dosing or treatment-emergent. Only TEAEs will be included in other AE listings, if not otherwise specified. A listing of AE will be provided for the combined placebo-controlled and LTE period.

Pre-treatment AE: AE starting before LTE first dose are considered pre-treatment AE for LTE period if it does not qualify for above TEAE definition i.e., no worsening.

Analysis period and analysis displays

Analysis period will be specified for each output. However, for either analysis period in this SAP (LTE period or placebo-controlled and LTE active treatment period), AE data will be summarized by LTE treatment group (5 LTE treatment groups as low-dose BIIB092 125mg/4weeks, low-dose BIIB092 375mg/12weeks, medium-dose, early start high-dose, late start high-dose, and BIIB092 total). Listings will include all data in placebo-controlled and LTE period (all data in the study), with an indicator of the study period (pre-dosing, placebo-controlled, or LTE) for each record when the event occurred.

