3.4 Dates and Points of Reference

The study day and baseline are defined for each analyses period respectively

1. LTE period

- Study Day 1: the date of the first dose of study treatment in the LTE period
- Study Day
 - For a date on or after Study Day 1

$$\text{Study Day} = (\text{Date of Interest}) - (\text{Study Day 1}) + 1$$
 - For a date before Study Day 1

$$\text{Study Day} = (\text{Date of Interest}) - (\text{Study Day 1})$$
- LTE baseline: the baseline value for the LTE period is defined as the most recent non-missing measurement collected prior to the first dose in the LTE period.
- Change from baseline will be defined as post-baseline value minus baseline value

2. Placebo-controlled and LTE period

- Study Day 1: the date of the first dose of study treatment in the PC period

CONFIDENTIAL

The information contained herein may not be used, disclosed, or published without the written consent of Biogen MA Inc.

- Study Day
 - For a date on or after Study Day 1
Study Day = (Date of Interest) – (Study Day 1) + 1
 - For a date before Study Day 1
Study Day = (Date of Interest) – (Study Day 1)
- PC and LTE baseline: the baseline value for the Placebo-controlled and LTE period is defined as the most recent non-missing measurement collected prior to the first dose in the PC period.
- Change from baseline will be defined as post-baseline value minus baseline value

3. Placebo-controlled and LTE active treatment period

- Study Day 1: the date of the first dose of BIIB092. For low-dose, medium-dose and early start high-dose subjects, this will be the date of first dose of BIIB092 in the placebo-controlled (PC) period; for late start high-dose subjects, this will be the date of first dose of BIIB092 in the LTE period.
- Study Day
 - For a date on or after Study Day 1
Study Day = (Date of Interest) – (Study Day 1) + 1
 - For a date before Study Day 1
Study Day = (Date of Interest) – (Study Day 1)
- Active treatment baseline: the baseline value for the active treatment period and is defined as the most recent non-missing measurement collected prior to study day 1.
- Change from baseline will be defined as post-baseline value minus baseline value

For data that are summarized by visit, assessment from all scheduled visits, EOS visit and unscheduled visits will be mapped to an appropriate analysis visit using a windowing scheme as describe in [Appendix I](#)

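### The LTE SAP's only treatment-emergence rule starts at the first LTE infusion, but the combined-period AE tables start early-start follow-up at the first placebo-controlled BIIB092 dose

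*SAP*

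**What the plan says.** **The emergence rule.** SAP 5.4.2 states: "A treatment-emergent AE is defined as AE that started or worsened after the start of first infusion of study treatment in LTE period". The rules for missing and partial start dates use the same reference, the first LTE dose. The section then sets a default: "Only TEAEs will be included in the tables, unless otherwise specified".

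**The outputs.** SAP 5.4.2.1 plans the overall AE summary for both the LTE period and the combined active treatment period. It adds: "Selected tables (marked with *) will be presented for incidence rate of AEs for the placebo-controlled and LTE active treatment period". Nine tables carry the asterisk. They cover all, severe, related and serious AEs. SAP 5.4.10 also plans COVID-19 AE tables for the combined period.

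**The combined period.**
- SAP 3.2 item 3 takes all placebo-controlled and LTE data of early-start subjects. It adds: "An example is the incidence rate of adverse events in the placebo-controlled and LTE active treatment period". It leaves out only subjects who had placebo and were never dosed in the LTE.
- SAP 3.4 item 3 sets Study Day 1 for the low-dose, medium-dose and early-start high-dose groups: "this will be the date of first dose of BIIB092 in the placebo-controlled (PC) period".
- SAP 5.4.2.2 starts follow-up at the "placebo-controlled period first dose of BIIB092 for early start subjects and LTE period first dose of BIIB092 for late start subjects".

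**The endpoint.** SAP 2.1 and protocol section 6 define the primary LTE endpoint as AE and SAE incidence over both periods. Protocol 16.3.2.1 ties emergence to the date of first dosing.

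**The concern.** For the combined tables the SAP counts events from one date and follow-up from another. In the four early-start groups, an AE that began under BIIB092 during the placebo-controlled period is not treatment-emergent under 5.4.2. It would count only if it worsened after the first LTE infusion or met a missing-date rule. The time in which it arose still counts as follow-up.

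Subjects randomised to BIIB092 who never entered the LTE are a sharper case. SAP 3.2 includes them, so they add follow-up, but they have no LTE dose against which onset or worsening can be tested. Only an AE with both dates missing would clearly qualify.

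Two programmers following different sections could produce very different tables for the primary LTE endpoint. The error under the literal rule runs one way. It lowers early-start rates and subject counts and leaves the late-start group unchanged, so the groups with the longest exposure would look safer than they are.

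**Working it through.** The documents give no AE count or rate on this point, so there is no figure to reproduce. The check compares the stated rules and then illustrates the size.

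**1. Is there a second rule?** SAP 5.4.2 names both analysis periods when it describes the displays, but defines emergence only once. Its pre-treatment AE definition is worded for the LTE period and has no combined-period counterpart. Infusion reactions (5.4.2.3) and AEs of special interest (5.4.2.4) are referred to the placebo-controlled SAP; treatment emergence is not. Laboratory shifts (5.4.3.2), ECG (5.4.5.1) and vital signs (5.4.6.1) use the placebo-controlled baseline for early start and the LTE baseline for late start. The AE section lacks this.

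**2. Follow-up that can yield no new event.** The LTE starts at Week 80, Day 561 (protocol Table 2), so 560 days come before it.
- To Week 100 (Day 701): 560/701 = 80%.
- To Week 226 (Day 1583): 560/1583 = 35%. SAP 5.6.2 says no subject reached Week 226, so 35% is a floor for anyone who entered the LTE.

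**3. Effect on the rate.** SAP 5.4.1.3 divides subjects with an event by total follow-up, and "Each subject will be counted only once within each category". Assume a constant hazard h per subject-year, equal across groups, and 80 weeks between the first placebo-controlled and first LTE doses. Let L be time in the LTE and T = L + 80 weeks, both in years.
- Early start, literal 5.4.2: (1 − e^(−hL))/T
- Early start, matched anchor: (1 − e^(−hT))/T
- Late start: (1 − e^(−hL))/L

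Ratio of literal to matched early-start rate:

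| Followed to | L (weeks) | h = 0.02 | h = 0.1 | h = 0.5 | h = 1.0 |
|---|---|---|---|---|---|
| Week 100 | 20 | 0.20 | 0.22 | 0.28 | 0.37 |
| Week 128 | 48 | 0.38 | 0.40 | 0.52 | 0.66 |
| Week 226 | 146 | 0.66 | 0.69 | 0.85 | 0.95 |

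Example at Week 100, h = 0.1: L = 20 × 7/365.25 = 0.383 and T = 100 × 7/365.25 = 1.917.
- Literal: 0.0376/1.917 = 1.96 per 100 subject-years, with 3.8% of subjects counted.
- Matched: 0.1744/1.917 = 9.10 per 100 subject-years, with 17.4% counted.
- Late start: 0.0376/0.383 = 9.81 per 100 subject-years.

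**4. Early/late comparison.** Literal early over late is L/(80 + L): 20/100 = 0.20 at Week 100, 48/128 = 0.38 at Week 128, and 146/226 = 0.65 at Week 226. Not all of this is the defect. With matched anchors the Week 100 ratio is already 0.98, 0.93, 0.71 and 0.54 at the four hazards, because longer follow-up lowers a once-per-subject rate.

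**5. Cross-check in days, rare-event limit.** LTE days over total days: 169/729 = 0.23 at Week 104, 505/1065 = 0.47 at Week 152, 1107/1667 = 0.66 at Week 238. If 20% of early-start subjects never enter the LTE and are followed to Day 631 (assumed):
- Week 104: 0.8 × 169/(0.8 × 729 + 0.2 × 631) = 0.19.
- Week 238: 0.8 × 1107/(0.8 × 1667 + 0.2 × 631) = 0.61.

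**The case against.** The best defence is that the TEAE-only rule is a default that yields to anything more specific. SAP 3.2 item 3 is more specific: it includes all early-start data and names the AE incidence rate. The pre-treatment definition is limited to the LTE period, the other safety sections use group-specific baselines, and the literal rule asks for an LTE dose from subjects who never had one. The authors probably meant the 5.4.2 definition for LTE-only tables.

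As evidence of intent this stands, but it does not supply a rule. Including all the data is not the same as saying which events are emergent or which date drives imputation. SAP 3.2 item 1 also pulls the other way, since it assigns the LTE period to all AE analyses.

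Several limits are fair:
- The one planned early-versus-late AE table (item 4 in 5.4.2.1) is LTE-only, and the SAE listing includes every SAE.
- Placebo-controlled AEs fall under a separate SAP not available here, so their loss from study reporting as a whole is not shown.
- Protocol 16.3.2.1 names no period, so the conflict with it is confined to the combined tables.
- SAP 5.4.2.2 makes the combined rates optional, although 5.4.2.1 commits to them and to the overall summary.
- The Week 100 case is weakly supported. The infusion bins in SAP 5.2.4 are "categories as integers from 1 to 20, and 1-5, 6-10, 11-15, 15-20, 21-26". A top value of 26 equals 20 placebo-controlled infusions plus the 6 from Week 80 to Week 100, but the bins overlap at 15 and may be unfinished text.

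**Conclusion.** The concern holds. The SAP's only emergence rule conflicts with its own definition of the combined active treatment period, and the affected tables report the primary LTE endpoint. It must be fixed.

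The size depends on the literal reading, assumed constant and equal hazards, and an 80-week gap between first doses. Under those assumptions the early-start rate falls to between 0.20 and 0.37 of its proper value at Week 100, and to between 0.66 and 0.95 at Week 226, over hazards of 0.02 to 1.0 per subject-year. The defect dominates for uncommon events, including most single SAE terms, and for short LTE follow-up. It is small for common events with long follow-up: at Week 226 and h = 1.0, 21.7 against 22.8 per 100 subject-years. LTE-period tables and the all-data listings are unaffected.

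**What to change.** Define treatment emergence by analysis period in SAP 5.4.2:
- **LTE-period tables:** first LTE infusion, as now.
- **Combined active treatment period:** first BIIB092 infusion, which is Study Day 1 in SAP 3.4 item 3. That is placebo-controlled Day 1 for early start and the first LTE infusion for late start.

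Apply the matching anchor to the missing-date rules, the partial start-date rules and the pre-treatment AE definition. State in 5.4.2.1, 5.4.2.2 and 5.4.10 which flag each table uses, and align SAP 3.2 item 1 with item 3.

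The cost is SAP wording and one extra TEAE flag in the AE dataset. No new data are needed.
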